8.5 Human Biological Samples

Instructions for the collection and handling of biological samples will be provided in the study specific Laboratory Manual. Samples should be stored in a secure storage space with adequate measures to protect confidentiality. For further details on Handling of Human Biological Samples see [Appendix G](#).

Samples will be stored for a maximum of 15 years from the date of the issue of the CSR in line with consent and local requirements, after which they will be destroyed/repatriated.

- Pharmacokinetic samples will be disposed of after the Bioanalytical Report finalization or 6 months after issuance of the draft Bioanalytical Report (whichever is earlier), unless consented for future analyses.
 - Pharmacokinetic samples may be disposed of or anonymized by pooling. Additional analyses may be conducted on the anonymized, pooled PK samples to further evaluate and validate the analytical method. Any results from such analyses may be reported separately from the CSR.
- Remaining ADA sample aliquots will be retained at AstraZeneca or its designee for a maximum of 15 years following issue of the CSR. Additional use includes but is not limited to further characterization of any ADAs, confirmation and/or requalification of

the assay as well as additional assay development work. The results from future analysis will not be reported in the CSR.

8.5.1 Pharmacokinetics

Serum samples will be collected for measurement of serum concentrations of tezepelumab as specified in the SoA (Section 1.3). Samples will be collected, labelled, stored, and shipped as detailed in the Laboratory Manual.

8.5.1.1 Determination of Drug Concentration

Samples for determination of tezepelumab concentration in serum will be assayed by bioanalytical test sites operated by or on behalf of AstraZeneca, using an appropriately validated bioanalytical method. Full details of the analytical method used will be described in a separate Bioanalytical Report.

Drug concentration information that may/would unblind the study will not be reported to investigative sites or blinded personnel until the study has been unblinded (see Section 6.3.4 for maintaining the study blind).

Incurred sample reproducibility analysis, if any, will be performed alongside the bioanalysis of the test samples. The results from the evaluation, if performed, will be reported in a separate Bioanalytical Report.

8.5.2 Immunogenicity Assessments

Blood samples for determination of ADA in serum from both tezepelumab and placebo groups will be assayed by bioanalytical test sites operated by or on behalf of AstraZeneca, using an appropriately validated bioanalytical method. Full details of the methods used will be described in a separate Bioanalytical Report.

ADA samples may also be further tested for characterization of the ADA response.

Samples will be collected, labelled, stored, and shipped as detailed in the Laboratory Manual.

8.5.3 Pharmacodynamics

Samples for the analysis of peripheral blood eosinophils will be performed in a central laboratory as part of the routine hematology assessment.

8.6 Human Biological Sample Biomarkers

Biomarker research is not applicable in this study.

8.7 Optional Genomics Initiative Sample

Optional Genomics Initiative research is not applicable in this study.

8.8 Health Economics OR Medical Resource Utilization and Health Economics

Health Economics/Medical Resource Utilization and Health Economics parameters are not evaluated in this study.

9 STATISTICAL CONSIDERATIONS

9.1 Statistical Hypotheses

No formal statistical hypotheses will be tested.

9.2 Sample Size Determination

The sample size justification is based on the desired precision of the estimate of the ratio of the GMTs (as $GMT_{vaccine} / GMT_{tezepelumab+vaccine}$). With 50 participants per arm, the 90% CI for the GMT ratio would be 0.67 to 1.48, assuming an observed ratio of 1, and that the log (post-dose HAI antibody titer or post-dose MN antibody titer) is normally distributed with a standard deviation (SD) of 1.2 on the natural log scale ([Langley et al 2013](#)).

9.3 Populations for Analyses

Antibody endpoints to the influenza vaccine—strain-specific HAI and MN antibody GMFRs and GMTs—will be analyzed using the vaccine immunogenicity analysis set. All remaining efficacy analyses will be performed using an ITT approach based on the full analysis set.

Demographic and baseline characteristics will be presented for both the full analysis set and the vaccine immunogenicity analysis set. Safety objectives and ADA will be analyzed based on the Safety analysis set. The population analysis sets are defined in [Table 10](#).

Table 10 Populations for Analysis

Population/Analysis set	Description
All participant analysis set	All participants screened for the study will be included in the 'All participant analysis set' and will be used for reporting of disposition and screening failures.
Full (ITT) analysis set	All participants randomized and receiving any study intervention will be included in the 'Full analysis set', irrespective of their CSP adherence and continued participation in the study. Participants will be analyzed according to their randomized treatment, irrespective of whether or not they have prematurely discontinued, according to the ITT principle. Participants who withdraw informed consent/assent to participate in the study will be included up to the date of their study termination.
Vaccine immunogenicity analysis set	All randomized participants who received the influenza vaccine plus at least 1 dose of tezepelumab or placebo, had pre and post-dose HAI or MN antibody measurements, had no influenza infection prior to Visit 7

Table 10 **Populations for Analysis**

Population/Analysis set	Description
	(Week 16), and had no protocol deviation, judged to have the potential to interfere with the generation or interpretation of an antibody response, will be included in the 'vaccine immunogenicity analysis set'. The analyses conducted using this analysis set will be based on the actual treatment received. Protocol deviations will be reviewed by the study team before unblinding at the primary database lock (Visit 7 [Week 16]).
Safety analysis set	All participants who received at least 1 dose of study intervention will be included in the safety analysis set. Participants will be classified according to the treatment they actually received. A participant who has on one or several occasions received active treatment will be classified as active. All safety and ADA summaries will be based on this analysis set.
PK analysis set	All participants who received tezepelumab and from whom PK blood samples were obtained and assumed not to be affected by factors such as CSP deviations will be included in the 'PK analysis set'. Those participants who had at least 1 quantifiable serum PK observation post first dose will be included in the PK analysis dataset. All PK summaries will be based on this analysis set.

Abbreviations: ADA=anti-drug antibody; CSP=clinical study protocol; HAI=hemagglutination-inhibition; ITT=intent to treat; MN=microneutralization; PK=pharmacokinetic.

Primary Analyses Estimands

Table 11 provides the parameters to follow for each set of primary analyses. **Please note:** If influenza vaccine administration is delayed, some participants' assessments at Week 12 and Week 16 may be performed at later timepoints.

Table 11 **Primary Analysis Estimands**

Primary Endpoints	Parameters

 Post-dose strain-specific hemagglutination-inhibition (HAI) antibody geometric mean fold rises (GMFRs) from Week 12 (pre-dose antibody measure) to Week 16 (EOT) Post-dose strain-specific microneutralization (MN) antibody GMFRs from Week 12 (pre-dose antibody measure) to Week 16 (EOT) Post-dose strain-specific serum HAI antibody geometric mean titers (GMTs) obtained at Week 16 (EOT) 	
Population: Vaccine immunogenicity analysis set, defined as all randomized participants who received the influenza vaccine plus at least 1 dose of tezepelumab or placebo, had pre- and post-dose HAI or MN antibody measurements, had no influenza infection prior to Visit 7 (Week 16), and had no protocol deviation judged to have the potential to interfere with the generation or interpretation of an antibody response.
 
Intercurrent Events: Treatment discontinuation: All data up to timepoint of post-dose antibody measurements will be included for participants in the vaccine immunogenicity analysis set.

Table 11 Primary Analysis Estimands

Primary Endpoints	Parameters

 Post-dose strain-specific serum MN antibody GMTs obtained at Week 16 (EOT) 	
Initiation of other medication: All data up to timepoint of post-dose antibody measurements will be included for participants in the vaccine immunogenicity analysis set.
 
Summary Measure: Least square geometric mean ratio estimates for placebo vs. tezepelumab and corresponding 90% CIs.


 Post-dose strain-specific antibody response at Week 16 (EOT) with antibody response defined as a \geq 4-fold rise in HAI antibody titer from Week 12 (pre-dose antibody measure) to Week 16 (EOT) Post-dose strain-specific antibody response at Week 16 (EOT) with antibody response defined as a \geq 4-fold rise in MN antibody titer from Week 12 (pre-dose antibody measure) to Week 16 (EOT) Post-dose strain-specific HAI antibody titer \geq 40 at Week 16 (EOT) Post-dose strain-specific MN antibody titer \geq 40 at Week 16 (EOT) 	
Population: Vaccine immunogenicity analysis set, defined as all randomized participants who received the influenza vaccine plus at least 1 dose of tezepelumab or placebo, had pre- and post-dose HAI or MN antibody measurements, had no influenza infection prior to Visit 7 (Week 16), and had no protocol deviation judged to have the potential to interfere with the generation or interpretation of an antibody response.
 
Intercurrent Events:
 
Treatment discontinuation: All data up to timepoint of post-dose antibody measurements will be included for participants in the vaccine immunogenicity analysis set.
 
Initiation of other medication: All data up to timepoint of post-dose antibody measurements will be included for participants in the vaccine immunogenicity analysis set.
 
Summary Measure: Number and % of participants in each treatment group meeting the specified threshold and corresponding 90% CI.

9.4 Statistical Analyses

There will be two database locks in this study. The primary database lock and analysis will be conducted after the last participant (enrolled in the 2021/2022 flu season) completes Visit 7 (Week 16), and the final database lock and analysis will be conducted once all participants have completed the follow-up period, Visit 8 (Week 28). All analyses of the primary objectives and selected safety objectives will be performed based on the primary database lock data.

The SAP will be finalized and signed-off prior to the primary database lock. It will include a more technical and detailed description of the statistical analyses described in this section. This section is a summary of the planned statistical analyses of the most important endpoints including primary and secondary endpoints.

9.4.1 General Considerations

All statistical analyses will be performed by Parexel International Biostatistics or other designated third-party providers, under the direction of the Biostatistics Group, AstraZeneca. Further details will be provided in the SAP. The SAP will be prepared prior to first participant randomized and any subsequent amendments will be documented, with final amendments completed prior to unblinding of the data. All statistical analyses presented in the CSP will be performed using the latest available version of SAS® (SAS Institute Inc., Cary, North Carolina, US), version 9.4 or higher.

All personnel involved with the analysis and conduct of the study will remain blinded until the primary database lock and important protocol deviations have been identified. After the primary database lock, treatment allocation for participants during this study will become known to the sponsor staff and designated CRO. The blind will be maintained for the investigator, investigational site staff, and for the participant.

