6.3.4 Ensuring Blinding

This is a double-blind study in which tezepelumab and placebo are not visually distinct from each other. All packaging and labelling of study intervention will be done in such way as to ensure blinding for all sponsor and investigational site staff. Neither the participant nor any of the investigators or sponsor staff who are involved in the treatment or clinical evaluation and monitoring of the participants will be aware of the treatment received. Since tezepelumab and placebo are not visually distinct, study intervention will be handled by a qualified person (eg, pharmacist or study nurse) at the site.

A Parexel site monitor will perform study intervention accountability. In the event that the treatment allocation for a participant becomes known to the investigator or other study staff involved in the management of study participants, or needs to be known to treat an individual participant for an AE, the sponsor must be notified immediately by the investigator and, if possible, before unblinding.

The following personnel will have access to the randomization list:

- Those carrying out the packaging and labelling of study intervention

- Those generating the randomization list (CALYX)
- Supply Chain Management department
- Patient Safety department at AstraZeneca
- Bioanalytical lab analyst performing the PK sample analysis

No other member of the extended study team at AstraZeneca, or any contract research organization (CRO) handling data, will have access to the randomization scheme during the conduct of the study until after the planned unblinding at the primary database lock after the last participant (enrolled in the 2021/2022 flu season) completes Visit 7 (Week 16).

The information in the randomization list will be kept from other personnel involved in the conduct of the study and in a secure location until the end of the study.

Maintaining the blind to the participant's blood eosinophil counts

While not entirely specific, participants on active tezepelumab treatment are expected to have lower blood eosinophil counts than participants on placebo. Procedures to mitigate unblinding on this basis include:

- From Week 4 onward, eosinophil, monocyte, and basophil counts will be redacted from central laboratory reports to prevent the investigator/designee from possibly deducing the eosinophil contribution to the complete blood count.

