- Participants will be assigned a unique identifier by the sponsor. Any participant records or datasets that are transferred to the sponsor will contain the identifier only; participant names or any information which would make the participant identifiable will not be transferred.

- The participant must be informed that his/her personal study-related data will be used by the sponsor in accordance with local data protection law. The level of disclosure and use of their data must also be explained to the participant in the informed consent/assent.
- The participant must be informed that his/her medical records may be examined by Clinical Quality Assurance auditors or other authorized personnel appointed by the sponsor, by appropriate IRB/IEC members, and by inspectors from regulatory authorities.

C 5 Committees Structure

The safety of all AstraZeneca clinical studies is closely monitored on an ongoing basis by Parexel representatives in consultation with Patient Safety. Issues identified will be addressed; for instance, this could involve amendments to the CSP and letters to investigators.

C 6 Dissemination of Clinical Study Data

A description of this clinical study will be available on <http://astrazenecagrouptrials.pharmacm.com> and <http://www.clinicaltrials.gov> as will the summary of the main study results when they are available. The clinical study and/or summary of main study results may also be available on other websites according to the regulations of the countries in which the main study is conducted.

C 7 Data Quality Assurance

- All participant data relating to the study will be recorded on eCRF unless transmitted to the sponsor or designee electronically (eg, laboratory data). The investigator is responsible for verifying that data entries are accurate and correct by electronically signing the eCRF.
- The investigator must maintain accurate documentation (source data) that supports the information entered in the eCRF.
- The investigator must permit study-related monitoring, audits, IRB/IEC review, and regulatory agency inspections and provide direct access to source data documents.

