 - Monitor the participant until liver biochemistry parameters and appropriate clinical symptoms and signs return to normal or baseline levels, or as long as medically indicated. Completes follow-up SAE Form as required.
 - Investigate the etiology of the event and perform diagnostic investigations as discussed with the Parexel Medical Monitor. This includes deciding which the tests available in the Hy's Law lab kit should be used.
 - Complete the 3 Liver eCRF Modules as information becomes available.

*A 'significant' change in the participant's condition refers to a clinically relevant change in any of the individual liver biochemistry parameters (ALT, AST or total bilirubin) in isolation or in combination, or a clinically relevant change in associated symptoms. The determination of whether there has been a significant change will be at the discretion of the investigator, this may be in consultation with the Parexel Medical Monitor if there is any uncertainty.

D 5 Review and Assessment of Potential Hy's Law Cases

The instructions in this section should be followed for all cases where PHL criteria are met.

As soon as possible after the biochemistry abnormality was initially detected, the Parexel Medical Monitor contacts the investigator in order to review available data and agree on whether there is an alternative explanation for meeting PHL criteria other than DILI caused by the study intervention, to ensure timely analysis and reporting to health authorities within 15 calendar days from date PHL criteria was met. The AstraZeneca Global Clinical Lead or equivalent and Global Safety Physician will also be involved in this review together with other subject matter experts as appropriate.

According to the outcome of the review and assessment, the investigator will follow the instructions below.

Where there is an agreed alternative explanation for the ALT or AST and TBL elevations, a determination of whether the alternative explanation is an AE will be made and subsequently whether the AE meets the criteria for a SAE:

- If the alternative explanation is **not** an AE, record the alternative explanation on the appropriate eCRF.
- If the alternative explanation is an AE/SAE: update the previously submitted Potential Hy's Law SAE and AE eCRFs accordingly with the new information (reassessing event term; causality and seriousness criteria) following the AstraZeneca standard processes.

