3.3 General Considerations

All statistical analyses will be performed by Parexel International, under the direction of the Late Stage Respiratory and Immunology Biometrics Group, AstraZeneca. All statistical analyses will be performed using the latest available version of SAS® (SAS Institute Inc., Cary, North Carolina, US), version 9.4 or higher.

All personnel involved with the analysis and conduct of the study will remain blinded until the primary database lock and important protocol deviations, have been identified. After the primary database lock, treatment allocation for participants during this study will become known to the sponsor staff and designated CRO. The blind will be maintained for the investigator, investigational site staff, and for the participant.

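### Protocol 9.4.1 and SAP 3.3 release allocation to sponsor staff and the CRO at the primary lock with no role limit, in conflict with parts of Protocol 6.3.4

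*Protocol*

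**What the plan says.** There are two database locks (Protocol 9.4, SAP 3.1): a primary lock after the last participant's Visit 7 (Week 16) and a final lock after Visit 8 (Week 28). Adverse events are collected through follow-up (Protocol 8.3.1).

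Protocol 9.4.1 and SAP 3.3 keep everyone engaged in analysis and conduct blinded up to the primary lock. They then state: "After the primary database lock, treatment allocation for participants during this study will become known to the sponsor staff and designated CRO". What survives the lock is narrower: "The blind will be maintained for the investigator, investigational site staff, and for the participant".

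Protocol 6.3.4 contains three statements on the same subject:

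- The opening paragraph gives no end date for its rule that the treatment received stays unknown to the people it lists: "Neither the participant nor any of the investigators or sponsor staff who are involved in the treatment or clinical evaluation and monitoring of the participants".
- On access to the list, "No other member of the extended study team at AstraZeneca, or any contract research organization (CRO) handling data, will have access to the randomization scheme" until the planned unblinding at the primary lock.
- The next sentence says the list is "kept from other personnel involved in the conduct of the study and in a secure location until the end of the study". Protocol 4.4 defines the end of the study as the last participant's last visit or procedure.

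Protocol 6.3.5 also ties code-breaking for the planned analyses to the primary lock. Protocol 6.3.4 separately gives some functions access to the list throughout, among them the sponsor's Patient Safety department.

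**The concern.** The release is defined by organisation, not by role, and the CRO named in these documents does more than statistics. Its biostatistics group performs the analyses (9.4.1). It also provides the site monitor (6.3.4) and the route for reporting serious adverse events (8.3.9). For a potential Hy's Law case, "the Parexel Medical Monitor contacts the investigator in order to review available data and agree on whether there is an alternative explanation" (Appendix D 5). Appendix C 5 describes study safety as "closely monitored on an ongoing basis by Parexel representatives in consultation with Patient Safety".

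If these people know the arm, the way they query, chase and discuss events after the lock could differ between arms, and allocation could reach a site that is meant to stay blind. The plan takes trouble elsewhere to prevent even inferred allocation: eosinophil, basophil and monocyte counts are redacted from central laboratory reports after Visit 3 and from communications with the sponsor. Releasing actual allocation to staff who speak with sites would undercut that safeguard.

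**Working it through.** The point is about text, so the main check sets the rules side by side.

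| Place | Who is covered | Blind or bar ends |
|---|---|---|
| Protocol 9.4.1, SAP 3.3 | Sponsor staff and CRO | Primary lock |
| Protocol 9.4.1, SAP 3.3 | Investigator, site staff, participant | Continues after the primary lock |
| Protocol 6.3.4, opening | Participant, investigators, sponsor staff in treatment, evaluation or monitoring | Not stated |
| Protocol 6.3.4, access bar | Sponsor's extended team, any CRO handling data | Primary lock |
| Protocol 6.3.4, next sentence | Other personnel in study conduct | End of study |
| Protocol 6.3.5 | Codes for the planned analyses | Primary lock |

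**Two test cases.** A sponsor physician who evaluates follow-up events is blinded without end under the opening of 6.3.4, but unblinded at the primary lock under 9.4.1. The CRO Medical Monitor is freed at the primary lock by 9.4.1 and by the access bar in 6.3.4. If the Medical Monitor counts among the other conduct personnel, the next sentence of 6.3.4 withholds the list until the end of the study. The documents do not settle either case.

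**Length of the exposed period** (nominal days from randomization, Protocol 1.3):

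- Visit 6 = 12 × 7 = 84; Visit 7 = 16 × 7 = 112; Visit 8 = 28 × 7 = 196.
- Visit 7 to Visit 8 = 196 − 112 = 84 days (12 weeks). The last participants therefore have up to 12 weeks left at the lock, less the time taken to lock, which is not stated.

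**Which tables are reached.** SAP 4.6.2.1 ends the on-treatment period no later than 33 days after the last dose.

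- With the last dose at Visit 6: 84 + 33 = day 117, which is 117 − 112 = 5 days after Visit 7.
- Follow-up counted only as on-study: 196 − 117 = 79 of the 84 days.

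Intensity and causality are tabulated for on-treatment events only (Protocol 9.4.3.1, SAP 4.6.2.2). Events after the lock fall almost wholly in the on-study tables by system organ class and preferred term.

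**Share of participants exposed.** The documents give neither the accrual period nor the time to lock. As an illustration only, assume even accrual over A weeks and a lock L weeks after the last Visit 7. The share with any follow-up left is (12 − L)/A. The share of all follow-up time that falls after unblinding is (12 − L)²/(24A).

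| A | L | Any follow-up left | Follow-up time after unblinding |
|---|---|---|---|
| 12 | 4 | 8/12 = 67% | 64/288 = 22% |
| 16 | 4 | 8/16 = 50% | 64/384 = 17% |
| 24 | 4 | 8/24 = 33% | 64/576 = 11% |
| 24 | 8 | 4/24 = 17% | 16/576 = 3% |

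Both shares are zero if L is 12 or more. Neither measures bias.

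**The case against.** The best defence is that the release was a deliberate choice, worded identically in protocol and SAP, and that 6.3.4 and 6.3.5 support it: the sponsor and CRO bar expires at the primary lock. On that view, the other personnel blinded until the end of the study are chiefly site staff, whom 9.4.1 also keeps blind. This much stands: 9.4.1 does not contradict 6.3.4 as a whole. But the reading leaves the opening of 6.3.4, which names sponsor staff and sets no end date, unreconciled, and it puts no limit on which CRO roles are unblinded.

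The defence is also right about consequences. Causality to study intervention is judged by the investigator, who stays blind. Helminth infections, injection site reactions and severe infections are taken from investigator entries. MedDRA-based definitions are fixed before the primary lock. The first report of a potential Hy's Law case is set to related by rule (Appendix D 4.2), and its biochemical criteria are objective. Patient Safety already has list access, so sponsor-side knowledge of allocation is not new at the lock. Safety summaries are descriptive and no hypotheses are tested.

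A reader might infer that the protocol unblinds the Medical Monitor and site monitors. No passage says so; the wording permits it because nobody is excluded. A reader might also infer that follow-up could no longer be called double-blind. The Synopsis describes the study as participant and investigator blinded, and that remains true after the lock.

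**Conclusion.** The point holds as an unrestricted release combined with inconsistent text. Protocol 9.4.1 and SAP 3.3 set no role limit, two sentences of 6.3.4 point the other way, and a third sentence of 6.3.4 agrees with the release. It follows that the CRO Medical Monitor and site monitors may be unblinded while dealing with blinded investigators on follow-up events.

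The exposure is confined to the querying and handling of late on-study events and to possible leakage to sites, for at most about 12 weeks per participant. The Week 12 and Week 16 antibody samples are drawn, and evaluability is decided, before unblinding, so the primary endpoints are not affected. Nor are almost all of the on-treatment causality tables; this assumes nominal visit days and a last dose at Visit 6. It would be tempting to quote a share such as two thirds of participants, but the accrual period and time to lock behind any such figure are assumptions. The change is worth making because it is cheap, and because the documents as they stand cannot show which roles reviewed follow-up safety data blinded.

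**What to change.** In Protocol 9.4.1 and SAP 3.3, state that at the primary lock allocation goes only to a listed analysis and reporting team. State that the Medical Monitor, site monitors and others who are in contact with sites or handle follow-up data stay blinded until the final database lock. Name the exceptions: emergency unblinding, unblinding for expedited reporting, and the functions already given list access in 6.3.4, including Patient Safety.

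Reword all three sentences of 6.3.4 (the opening statement on sponsor staff, the access bar that lapses at the primary lock, and the end-of-study sentence) so that each names the same roles and the same end points.

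The cost is an access list and a few aligned sentences across the two documents. The CRO would have to keep its analysis and monitoring teams separate for up to about 12 weeks.
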